3.3 Study Duration

It is anticipated that the overall duration of the pivotal phase of the AFRS study will be approximately 8 years. This estimate is based upon a projected patient enrollment period of 4-5 years, including the period of time (~2 years) under the previous sponsor, Facet Solutions. Follow-up visits will occur for the subsequent 24 months while all patients reach the 24 month postoperative time point, with data analysis and report generation accounting for an additional 4-6 months. The follow-up period may increase up to 10 years as needed to address postmarketing studies that may be required by the FDA during the approval process.

3.4 Control Procedure

Upon completion of the decompression procedure, patients randomized to the control procedure will undergo an instrumented posterolateral fusion (PLF), Autograft bone recovered from the decompression procedure and/or the iliac crest, if necessary, will be used to support the fusion procedure. The autograft will be supported with allograft bone, including demineralized bone matrix, as needed based on the Investigator's determination of required volume. The use of bone morphogenetic protein (BMP) will be prohibited.

[REDACTED]

[REDACTED]

[REDACTED]

3.5 Study Endpoints

3.5.1 Primary Endpoint

The primary study endpoint for this study is individual patient success at 24 months. Individual patient success will be defined as follows and each component of the primary endpoint will be adjudicated by the Clinical Event Committee:

- Improvements in the ZCQ score by a minimum decrease of 0.5 versus baseline for both Symptom Severity (SS) and Physical Function (PF) scores.
- Maintenance or improvement in neurological outcome at 24 months.
- No subsequent surgical intervention at the level of treatment (including device failures requiring revision, removal, re-operation and supplemental fixation).
- No serious device-related adverse events (see paragraph below.)

[REDACTED]

[REDACTED]

[REDACTED]

[REDACTED]

[REDACTED]

[REDACTED]

[REDACTED]

4.0 PATIENT SELECTION AND ENROLLMENT

All patients presenting with acquired degenerative lateral, lateral recess and/or central canal stenosis at a single level from L3 to S1 who require decompression and facetectomy and have failed to improve with at least six months of conservative treatment are potential study candidates and will be approached for consent prior to any data collection by a member of the institution's research team. A screening and enrollment log will be provided to study sites to maintain a cumulative log of all screened patients.

Every effort will be made to establish eligibility of the participants prior to enrollment. Only patients who meet all eligibility criteria and have signed an IRB/IEC approved consent form are considered to be enrolled in the study. Patients who are consented but not randomized or randomized but are withdrawn prior to initiation of surgical procedures are considered a screen failure for this study. Reasons for screening failure will be documented on the site screening log. All treated patients will be evaluated, as defined by protocol through 24 months, and annually thereafter as required by FDA.

Patients may not be enrolled in the AFRS study without first granting their consent. No study specified procedures may be completed until patient has signed an approved Informed Consent form. The informed consent process is accomplished by providing the patient with a copy of and allowing the patient adequate time to review, the Informed Consent Form. The contents of this form are discussed by the participating clinical trial site staff with the patient, while allowing adequate time for questions. Patients indicate they are willing to participate in the study, by signing and dating the site's current IRB/IEC approved Informed Consent form.

A patient should not sign the Informed Consent Form if s/he is not willing to accept either the investigational or control treatment as established by the randomization process. Following consent, the patient will be randomized into either the AFRS (investigational) or posterolateral fusion (control) group.

All patients screened for this study should be recorded but only consented patients will receive a study number. All consented patients will be assigned a unique patient number where the first two digits represent the investigative site and the last three digits represent the patient number (e.g. 01-001 represents the first consented patient at site 01). Patients are considered enrolled only after they have signed the informed consent and met all eligibility requirements. Patients will be identified by this assigned number for the duration of their participation in the study.

Randomization will be performed on a per-patient basis, blocked by center to maintain a 2:1 mix of patients in the investigational and control groups at each institution. Randomization must occur prior to surgery and only after the patient provides written informed consent, completes all baseline procedures and meets the requirements of the study inclusion and exclusion criteria. Sites are reminded that enough time should remain between randomization and surgery to allow sufficient time for insurance authorization.

As specified earlier, each Investigational Site may complete up to two training cases in advance of randomizing patients into the study. These cases provide an opportunity for the Investigator to become familiar with the technique and instrumentation. Training cases will not be randomized but will be followed per the protocol and analyzed as a separate population.

Any patient enrolled, whether randomized or not, will be assigned a patient number. The reason for failure to randomize or failure to treat will be recorded in his/her study records. For enrolled (consented & eligible) patients who **are not** treated, the following information will be recorded in the patient's study file:

- Demographic information
- Inclusion/exclusion criteria
- Reason for failure to randomize

If a randomized patient is withdrawn prior to treatment, the next patient will be assigned the next randomly determined treatment as per the study randomization plan until a sufficient number of patients have been treated per each group.

All patients treated in the study are considered to be "follow-up eligible" and will be required to adhere to the follow-up schedule as outlined in **Appendix 1**. Patients that withdraw consent after receiving treatment will not be required to undergo follow-up after withdrawal; however, these patients will still be considered part of the patient cohort. No patient will be removed from the study unless the patient has withdrawn his or her consent before treatment or no treatment was ever attempted.

4.1 Inclusion/Exclusion Criteria

Before entry into this study, each patient will be evaluated by the investigator to determine if s/he satisfies the eligibility criteria for this trial. To be eligible, the patient must meet all of the characteristics in the "Inclusion Criteria" and none of the characteristics listed in the "Exclusion Criteria" as listed below.

4.1.1 Inclusion Criteria

- 21-85 years of age and skeletally mature;
- Undergone at least six cumulative months of conservative treatment prior to surgery including any of the following: medications, NSAIDs, physical therapy, bracing, chiropractic manipulation, modified activities of daily living, epidural injections, facet block injections;
- Lateral, lateral recess and/or central canal stenosis as demonstrated by compression of the thecal sac and/or cauda equina, nerve root impingement by either osseous or non-osseous elements or evidence of hypertrophic facets with encroachment into the central canal or lateral recess at the involved level as determined by MRI, CT scan, plain film or myelography;
- Disc height measuring ≥ 4 mm at the operative level;
- Persistent leg, thigh and/or buttock symptoms, including pain, numbness, burning or tingling with a minimum leg pain score of 40mm as measured with the VAS;

- Score greater than 2 on a scale of 1-5 on the ZCQ Symptom Severity Score
- Score greater than or equal to 2 on a scale of 1-4 on the ZCQ Physical Function Score;
- Candidate for a decompression with full facetectomy at the operative level;
- Candidate for an instrumented posterolateral fusion;
- Willing and able to comply with postoperative and routinely scheduled clinical and radiographic evaluations;
- Lives in the immediate area and has no plans to relocate to another geographic area before the completion of the study, or lives outside the immediate area and is willing to comply with scheduled postoperative visits with a designated physician;
- Has signed a patient informed consent, specific to this study.

4.1.2 Exclusion Criteria

- Previous surgical procedure at the operative or adjacent level except for one of the following: micro-discectomy, laminectomy, lamino/foraminotomy, rhizotomy, IDET, and/or interspinous spacer;
- Previous lumbar fusion or disc replacement procedure;
- Osteoporosis as defined by Simple Calculated Osteoporosis Risk Estimation (SCORE) screening questionnaire score of 6 or greater and DEXA bone density measured T-score ≤ -2.0 ;
- Greater than Grade I spondylolisthesis or retrolithesis, as defined by the Meyerding Grading Classification, at the operative level;
- Spondylolisthesis any grade, as defined by the Meyerding Grading Classification at levels other than at the operative level;
- Scoliosis of the lumbar spine (defined as more than 11° Cobb angle), as indicated by plain X-ray films;
- Primary diagnosis of discogenic back pain due to torn, herniated, inflamed or irritated disc or other pathology where the patient exhibits axial back pain from degenerative disc disease;
- Acute traumatic pars fracture at the operative or adjacent level vertebral body;
- Spinal stenosis at more than three lumbar segments;
- Experienced acute trauma to the lumbar spine within the last 24 months;
- Active infection at the operative level, or a systemic infection including prior or pending treatment for HIV or Hepatitis C;
- Physically or mentally compromised (*i.e.*, being currently treated for a psychiatric disorder, senile dementia, Alzheimer's disease, presence of alcohol or substance abuse) in a manner that would compromise his or her ability to participate in the clinical study;
- Diagnosed systemic disease (*i.e.*, Paget's disease, muscular sclerosis, amyotrophic lateral sclerosis (ALS), renal osteodystrophy, metastasis to vertebrae, Lupus, or ankylosing spondylosis) that may affect the patient's welfare or overall outcome of the research study;

- Immunologically suppressed or immunocompromised;
- Insulin-dependent diabetes mellitus (type I diabetes);
- Currently undergoing long-term steroid therapy (treated in the last 6 months with systemic corticosteroids);
- Metabolic bone disease (i.e., osteomalacia, and/or osteogenesis imperfecta);
- Is of child-bearing potential, and is either pregnant or interested in becoming pregnant during the duration of the study;
- Medically significant obesity as defined by a Body Mass Index (BMI) of > 40 kg/m². BMI = (weight in pounds \times 703) \div (height in inches \times height in inches);
- Active malignancy: a history of any invasive malignancy (except non-melanoma skin cancer), unless the patient has been treated with curative intent and there have been no clinical signs or symptoms of the malignancy for at least 5 years;
- Known allergy to cobalt chromium or titanium;
- Used any investigational drug or device within the past 30 days;
- Pending litigation related to back pain or injury;
- Is a prisoner.

5.0 STUDY PROCEDURES

The AFRS device will be clinically evaluated utilizing a standardized protocol as described below. The protocol has been designed to minimize variations in patient selection, surgical technique, postoperative management, patient evaluation, and documentation of results. To further assure consistency, each investigator will be trained in all aspects of the protocol, including the surgical technique and appropriate documentation.

Study patients will be evaluated pre-operatively, postoperatively and upon discharge, and at 6-weeks, 3, 6, 12 and 24 months postoperatively. In addition, patient follow-up will be completed annually after the 24-month time point as required by the FDA. The evaluations to be completed at each study visit will include radiographic, pain, function and neurological assessments. A summary of the data collection requirements is presented in **Appendix 1**. Included in the summary is a list of acceptable time windows for patient follow-up to be completed at each study time point. A detailed description of the assessment to be performed at each study visit is provided below.

5.1 Screening/Pre-Procedure

Patients presenting with stenosis will potentially be eligible for participation in the study. Before being considered for enrollment into this clinical evaluation or receiving any study-specific diagnostic tests and/or questionnaires to further determine eligibility, the Informed Consent Form must be completed and signed by the patient.

Once an Informed Consent Form has been successfully completed, the patient will be evaluated for his or her ability to meet the inclusion and exclusion criteria. Only those individuals who meet all of the inclusion criteria and none of the exclusion criteria are to be enrolled in the study. A list of consented patients excluded from enrollment into this study, or considered patient screen failures will be maintained for each investigation site. The following screening procedures and baseline data are collected for all patients.

5.1.1 Patient History

Patient demographics and medical history will be completed by the physician or assigned medical personnel. Specific parameters include:

- Age
- Gender
- Height/weight
- Smoking status
- Work status
- Education level
- Duration of pain
- Concurrent health conditions
- Medication use
- Previous surgeries/treatments

- Previous conservative treatment modalities

The patient should demonstrate failure to improve with conservative, non-surgical treatment for a minimum period of six months. Conservative, non-surgical treatment options may include, but is not limited to, medications, NSAIDs, physical therapy, bracing, chiropractic manipulation, modified activities of daily living, epidural injections, facet block injections;

Those patients who are smokers will be advised that they need to stop smoking for a period of 6 weeks after the procedure in order to be eligible for study participation.

Female patients of childbearing potential must have a negative pregnancy test within 14 days prior to treatment and must agree to avoid pregnancy during the course of the study

For those patients that enter the study with a previous surgery, information is collected on the case report form to provide as much detail as possible on the nature of the surgery including type, date, parameters of bone or device removal or other information that may be useful in analyzing the procedure and its affect on the patient.

A comprehensive physical examination will be conducted at baseline and any abnormal findings will be recorded on the CRF. Physical examinations at follow-up visits will be symptom directed only.

5.1.2 MRI, CT Scan, Plain Film, Myelography

Radiographic methods will be completed pre-procedure to verify the presence of lateral, lateral recess and/or central canal stenosis per the criteria outlined in inclusion/exclusion section above. If a study candidate has received a CT scan or MRI of his/her spine within six months prior to study screening, the Investigator may use CT/MRI to verify study eligibility for this criteria.

5.1.3 DEXA Scan

Patients will be administered the Simple Calculated Osteoporosis Risk Estimation (SCORE) questionnaire. Those patients who receive a total score of 6 or greater will need to have a DEXA scan completed. Patients with a T-score equal to or less than (-) 2.0 will be excluded from the study. If a study candidate has received a DEXA scan of his/her spine within the previous six months of study screening, the Investigator may use the T-score results to determine study eligibility for this criteria.

5.1.4 Disc Height

Radiographic assessment of the disc height will be used to screen out patients with a compromised disc and potential degenerative disc disease. The operative-level disc height must be greater than or equal to 4.0 mm in order for patients to qualify for enrollment into the study. For the purposes of patient eligibility the determination of this measurement will be made by the Investigator.

5.1.5 Radiographic Assessment

The following radiographs will be taken during pre-procedure screening to establish a baseline for future follow up visits:

View	Position	Image Type
Lateral	Standing Neutral	Lateral
Lateral	Flexion-Extension	Flexion, Extension
AP	Standing Neutral	AP
AP	Lateral Bending	Left Lateral Bending, Right Lateral Bending

The radiographs will be independently evaluated for the following quantitative measurements at the operative and adjacent levels:

- Range of Motion: Calculated from the flexion-extension and lateral bending radiographs
- Intervertebral Translation: Calculated from the flexion-extension radiographs
- Disc Height: Calculated from the static lateral and AP radiographs.

The recommended radiographic protocol detailing the procedures is found in **Appendix 2**.

5.1.6 Function

A pre-operative assessment of function will be made to establish a baseline for comparison to postoperative results. Specifically, the patient will complete the ZCQ and ODI questionnaires in order to measure pain and function. These forms are completed by the patient only.

5.1.7 Neurological Assessment

A neurological assessment¹⁵ will be completed and is performed by the physician or designee (as specified on the site delegation/ signature log). Whenever possible, every effort should be made to use the same individual to perform a patient neurological assessment for the duration of the study. Specific pre-operative neurological evaluation parameters include:

- Reflexes (patellar (L2, L3, L4) and Achilles tendon (S1)) will be measured (left and right) and recorded using a 3-point scale: 0 (absent, trace); 1 (normal) or 2 (hyperreflexic, clonus).
- Straight Leg Raising (SLR) (L4, L5) will be measured (left and right, sitting and supine) and recorded using a 2-point scale: 0 (0°-70° positive test) or 1 (70°+ negative test).

- Sensory Function will be measured by nerve root distribution using a light touch technique with results recorded using a 2-point scale: 0 (decreased, anesthetic or hyperesthetic) or 1 (normal). The following dermatomes will be evaluated based on level of use:

L1	Anterior Quadriceps
L2	Anterior Thigh
L3	Anterior Knee
L4	Medial Foot
L5	Dorsal Foot
S1	Lateral Foot

A figure detailing the location of the required dermatomes is located in **Appendix 3**.

- Muscle Strength will be measured for individual muscle groups and recorded using a 5-point scale: 0 (No evidence of contractility), 1 (Slight contractility, no joint motion), 2 (Joint motion with gravity eliminated), 3 (Some joint motion against gravity), 4 (Full joint motion against gravity, some resistance) or 5 (Full joint motion against gravity, full resistance).

The following muscles will be evaluated based on the level of use using the noted motor evaluations:

L1-L2	Iliopsoas	Hip Flexion
L2-L4	Quadriceps	Knee Extension
L4-L5	Anterior Tibial Group	Ankle Dorsal flexion
L4-S1	Gluteus Maximus	Hip Extension
L5	Hallucis Longus	Great Toe Dorsiflexion
L5-S1	Hamstrings	Knee Flexion
S1	Flexor Hallucis	Ankle Plantar Flexion

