5.6.3 Neurological Assessment

The neurological assessment will be completed and is performed by the physician or designee as specified on the site delegation/ signature log. Whenever possible, every effort should be made to use the same individual to perform a patient neurological assessment for the duration of the study. The specific postoperative neurological evaluation parameters are outlined in section 5.1.7 above. The evaluation will be completed at 6 weeks, 3, 6, 12 and 24 months, and annually as required by FDA. A decrease in any one of the measures compared to baseline will be considered an adverse event and should be documented on the appropriate CRF.

For the purposes of determining patient success for the primary endpoint, a successful neurological outcome is defined as: Maintenance or improvement in sensory, motor function, reflexes and muscle strength.

The results of this exam will be adjudicated by the CEC for the purposes of defining patient success.

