5.6.9 Adverse Events

Adverse events (AEs), including Serious Adverse Events (SAEs), will be captured intraoperatively and during all study follow-up visits. Adverse event definitions and reporting requirements are detailed in Section 6.0: Adverse Event Reporting. All reported AEs will be followed until resolution or completion of the study or postmarket study, as required by FDA.

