6.0 ADVERSE EVENT REPORTING

6.1 Adverse Events

An Adverse Event (AE) is defined as any undesirable clinical occurrence in a patient, whether it is considered to be device-related or not. Adverse events may occur intraoperatively or postoperatively, and are reported on the Adverse Event Form (SA10). Conditions that existed or occurred prior to treatment in this study may only be considered adverse events if the patient’s condition worsens or requires additional treatment.

AEs will be classified and tabulated by the following:

1. Their relationship to the investigational device (AFRS implant) or control (posterolateral fusion) procedure, depending on the patient’s randomization into the trial;
2. Their relationship to the AFRS implant (investigational arm) or posterolateral fusion hardware (control arm) itself,
3. The severity of clinical event;
4. The action taken to treat the event; and
5. The outcome of the event.

Serious adverse events and deaths are considered adverse events, and will be listed and reported separately. Unanticipated adverse device effects will be recorded and reported in accordance with FDA regulations.

The determination of whether an adverse event is classified as a Serious Adverse Event (SAE) or Unanticipated Adverse Device Effect will be based on the definitions contained in this section, while also taking into account the clinical judgment of the investigator.

Adverse events will be coded by the Clinical Events Committee, based on the body system (e.g. gastrointestinal) and categorization of events appropriate to the condition.

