6.1.1 Adverse Event Term

An adverse event term is determined by the investigator/site coordinator, based on the patient’s symptom or condition, and is described on the form. Potential adverse events may include, but are not limited to, the following:

- Implant breakage;
- Component disarticulation;
- Component degradation;
- Implant displacement/dislocation;

- Pedicle disruption/failure;
- Allergic reaction to implant materials;
- Reaction to implant wear debris;Fracture/damage to pedicle;
- Fracture/damage to spinous process;
- Failure of bone to heal around implant;
- Bone resorption;
- Non-union, delayed union;
- Bursitis;
- Vessel damage/bleeding;
- Nausea and/or vomiting;
- Superficial infection;
- Deep wound infection;
- Hematoma at surgical site;
- Incisional pain;
- Pulmonary embolism;
- Stroke;
- Myocardial infarction;
- Coronary episode;
- Pneumonia;
- Kidney failure;
- Bowel obstruction
- Dural tear;
- Thrombosis;
- Nerve injury;
- Neuropathy
- Cauda equina syndrome;
- Transverse process fracture;
- Pseudomeningocele;
- Paralysis;
- Spinal fluid leakage;
- Spinal cord damage;
- Bone fracture;
- Spinous process fracture;
- Spondylosis;
- Heterotopic bone formation;
- Scoliosis;
- Kyphosis;
- Segmental instability;
- Decrease in neurological function;
- Worsening leg and/or back pain;
- Worsening pain associated with stenosis;
- Degeneration at adjacent level(s);

- Respiratory distress;
- Wound dehiscence;
- Wound swelling;
- Death

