9.1 Surgical Risks

[figure not shown]
There are risks related to any surgical procedure as well as procedures specific to spinal intervention. Surgical risks associated with this procedure include: vessel damage/bleeding; superficial infection; deep wound infection; hematoma at surgical site; incisional pain; pulmonary embolism; stroke; myocardial infarction; coronary episode; pneumonia; kidney failure; bowel obstruction; dural tear; thrombosis; nerve injury; cauda equina syndrome; transverse process fracture; pseudomeningocele; paralysis; spinal fluid leakage; spinal cord damage; bone fracture; spinous process fracture; spondylosis; heterotopic bone formation; scoliosis; kyphosis; segmental instability; decrease in neurological function; worsening back pain; worsening pain associated with stenosis; respiratory distress; wound dehiscence; wound swelling.

It is expected that the risks and complication rates strictly associated with the procedure would be similar to those associated with other posterior fixation procedures.

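### The neurological adverse event rule in 5.6.3 misfires for reflexes: normal is the middle code, so a decrease flags a return from hyperreflexia to normal and gives no trigger for new hyperreflexia or clonus

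*Combined protocol and SAP*

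**What the plan says.** Section 5.1.7 sets out four neurological measures, each with a numeric code. Reflexes (patellar and Achilles, left and right) are "recorded using a 3-point scale: 0 (absent, trace); 1 (normal) or 2 (hyperreflexic, clonus". Sensory function is "0 (decreased, anesthetic or hyperesthetic) or 1 (normal", which puts reduced and heightened sensation together in the abnormal code. Straight leg raising is 0 for a positive and 1 for a negative test. Muscle strength runs from 0 (no contractility) to 5 (full resistance).

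Section 5.6.3 carries these measures into follow-up: "The specific postoperative neurological evaluation parameters are outlined in section 5.1.7 above". It then gives the reporting rule: "A decrease in any one of the measures compared to baseline will be considered an adverse event". No direction is set for reflexes.

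Section 6.1 limits what counts when a finding was already present: "Conditions that existed or occurred prior to treatment in this study may only be considered adverse events" if the condition gets worse or needs further treatment. Section 5.6.9 points to the same place: "Adverse event definitions and reporting requirements are detailed in Section 6.0". Section 8.7 tabulates adverse events by arm, with 95% credible intervals for the difference in proportions.

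**The concern.** A rule based on a decrease works only if a lower code is always a worse state. That is true of straight leg raising, sensory function and strength. It is not true of reflexes, where the two kinds of abnormality lie on either side of normal. A patient who enters with hyperreflexia and normalises has a lower code; a patient who enters normal and develops clonus has a higher one. Applied as worded, the rule reports the first and is silent on the second.

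What is at stake is consistent recording. One site may go by the codes and record normalised reflexes as adverse events, with no specific prompt for new hyperreflexia or clonus. Another may read the sentence as clinical worsening and do the reverse. The same finding could then enter the 8.7 tables differently across up to 30 sites.

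**Working it through.** The plan states no figure on this point, so the check is an enumeration from the scales.

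**Inputs.** The reflex, straight leg raise, sensory and strength codes (5.1.7); the decrease rule (5.6.3); the pre-existing-condition rule (6.1).

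**Method.** Let B be the baseline code and F the follow-up code. Applied to the codes, the rule flags an adverse event when F < B. For reflexes, distance from normal is d = |code − 1|. A change is a worsening if d rises, an improvement if d falls, and a move between abnormal states if d stays at 1.

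**Reflexes.** There are 3 × 3 = 9 pairs, of which 3 are no change and 6 are changes:

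| B to F | d | Direction | Flagged (F < B)? |
|---|---|---|---|
| 1 to 0 | 0 to 1 | worsening | yes, correct |
| 1 to 2 | 0 to 1 | worsening | no, missed |
| 0 to 1 | 1 to 0 | improvement | no, correct |
| 2 to 1 | 1 to 0 | improvement | yes, misdirected |
| 2 to 0 | 1 to 1 | between abnormal states | yes |
| 0 to 2 | 1 to 1 | between abnormal states | no |

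Four changes start or end at normal, and 2 of these 4 are misdirected. The two moves between abnormal states are treated differently from each other. Both routes into code 2 (1 to 2 and 0 to 2) go unflagged.

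**Other scales.** With k codes and the best state highest, there are k(k − 1) changes, half of them downward.

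- Straight leg raise: 2 × 1 = 2 changes, 0 misdirected.
- Sensory: 2 × 1 = 2 changes, 0 misdirected.
- Strength (six listed codes, 0 to 5): 6 × 5 = 30 changes; all 15 worsenings are flagged, none of the 15 improvements is, so 0 misdirected.

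**Against 6.1.** For 2 to 1, the finding was present before treatment and has resolved. Section 6.1 would exclude it unless it needed further treatment; 5.6.3 as worded includes it. For 1 to 2 and 0 to 2, 5.6.3 is silent, and reporting depends on the site judging the change to meet the general definition in 6.1.

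**The other reading.** If decrease means clinical worsening, flag when d rises: 1 to 0 and 1 to 2 are flagged, 0 to 1 and 2 to 1 are not, and 0 of 4 are misdirected. Moves between 0 and 2 remain undefined.

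**Opportunities, not events.** Two reflexes × two sides × five visits to 24 months gives 20 baseline comparisons per patient with complete follow-up: 20 × 300 = 6,000 to 20 × 750 = 15,000 across the planned sample sizes. The documents give no reflex frequencies, so the number of comparisons affected cannot be obtained.

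**The case against.** The strongest reply is that the sentence never mentions codes. An examiner may take a decrease to be a clinical loss, and the protocol's own vocabulary supports this: 6.1.1 lists "Decrease in neurological function" among the potential events and 9.1 lists "decrease in neurological function" among the surgical risks. With 5.6.9 sending readers to Section 6.0, the two sections can be read together: 6.1 excludes the return to normal and captures new clonus that is clinically undesirable. The codes are collected at every follow-up visit in any case. The case report form and the source cited for the neurological assessment, neither of which can be seen here, might settle the reading.

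Much of this stands. It limits the consequence: new clonus loses a specific trigger, but remains reportable. It does not remove the defect. Section 5.6.3 speaks of the measures, which 5.1.7 records as numbers, not of function overall. Even in ordinary language, new clonus is not a decrease in a reflex. The harmonised reading has to be brought in from elsewhere, because 5.6.3 does not state it. Nor does the Clinical Events Committee clearly close the gap: the visible text has it adjudicate the examination for patient success, code adverse events, and classify their severity, relatedness and anticipated nature. It does not have it decide whether a reflex change is recorded as an event.

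A reader might infer more than the documents support:

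- **That the reflex coding corrupts the primary endpoint or the 8.7 neurological test.** Success is defined in words (status maintained or improved) and adjudicated by the committee. Text after 3.5.1 is redacted and section 8.8 cannot be read in this copy. No visible analysis uses the reflex code numerically.
- **That 2 of 4 is a 50% error rate.** It counts kinds of change, not patients or events.
- **That one arm is favoured.** The rule is the same in both arms, and randomisation is stratified by site.

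**Conclusion.** The point holds as a wording defect in 5.6.3 that is confined to reflexes. As worded, the rule flags 2 to 1 against the sense of 6.1, and gives no trigger for 1 to 2 or 0 to 2. The conclusion rests on applying the sentence to the 5.1.7 codes, which its text invites but does not require; if decrease means clinical worsening, the reversal disappears. The consequence is inconsistent recording of adverse events between sites. Its size cannot be derived and may be small. The documents show no error in the primary endpoint and no bias between arms. It should be corrected because the remedy is cheap, but it does not threaten the trial's main conclusion.

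**What to change.** In 5.6.3:

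- Replace *decrease* with *worsening*.
- State that for reflexes a worsening is a move away from code 1, and that a move to code 1 is not an adverse event.
- State one rule for changes between 0 and 2 that applies in both directions.
- Reconcile the sentence with 6.1, so that a reflex returning to normal is not recorded as an event and new hyperreflexia or clonus has an explicit trigger.

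The other three scales need no change, and no new data are needed. The cost is a short clarification to sites and, since section 3.3 shows that enrolment was under way before this revision, a check of reflex-based adverse events already recorded against the reflex codes already collected.
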